Study Population: This study focuses on young adult (YA) cancer survivors, targeting ~150 participants total enrolled. Inclusion criteria included: 18-39 years old, within 3 years of completing primary treatment or on maintenance chemotherapy, English-speaking, US resident, and smartphone access. Exclusion criteria were: cancer recurrence since treatment completion, central nervous system cancer diagnosis (to ensure requisite cognitive functioning), in hospice, and prior diagnoses of alcohol/drug dependency, psychosis, bipolar disorder, or major depressive disorder.

Study Design: 2-arm randomized controlled trial (RCT) assessing the feasibility, acceptability, and preliminary efficacy of 'Achieving Wellness After Reaching the End of Treatment' – or AWARE – a digital intervention with health coaching that targets hope, compared to an attention control (AC; randomized at a 1:1 ratio), among 155 YA cancer survivors.

Sample Size: 155 participants

Study Duration: Participants are involved in an 8-week digital, coach-assisted intervention and asked to complete assessments at baseline and 2- and 4-month follow-up.

Primary Objective: Assess the feasibility and acceptability of AWARE vs. AC

Secondary Objectives: Assess the preliminary efficacy of AWARE vs. AC

Background and Significance:

Addressing the needs of young adult (YA) cancer survivors (ages 18-39) is crucial, given the ~80,000 US YAs diagnosed annually,¹ their high survival rates,¹ and the multiple challenges (e.g., physical, emotional, social, occupational, financial) they face post-treatment within this pivotal developmental period.²⁻⁴ Thus, research is needed to develop effective interventions addressing YA survivors' psychosocial needs and quality of life (QOL) during the survivorship journey.⁵

Historically, YA survivorship intervention research has largely focused on physical needs and, perhaps relatedly, defined target populations by cancer site. More recently, research has focused on psychosocial needs of cancer survivors, including pediatric, adolescent, and YA (AYA) survivors.⁶⁻⁹ A 2022 meta-analysis identified 61 psychosocial, behavioral, and supportive interventions for pediatric and AYA survivors (1987-2020)¹⁰ and documented moderate effects for certain outcomes (i.e., physical symptoms, mental health, social, general QOL) but not others (i.e., cognitive, academic, cancer-related knowledge). This study identified 16 trials focused on AYAs; only 5 had a mean age >18 and only one had a sample size >100.¹⁰ Moreover, findings indicated that interventions for AYA (vs. pediatric) survivors were less effective.¹⁰

Notably, psychosocial interventions for cancer survivors have often targeted mental health outcomes (e.g., depression, anxiety) rather than positive outcomes.^{8,10,11} Interventions targeting positive outcomes for YA survivors may draw from positive psychology.¹² Hope, which can be defined in several ways, is a particularly relevant construct.^{9,13} One well-published definition, developed by Snyder et al.,^{14,15} suggests that hope involves cognitive skills to: 1) establish values-based, meaningful goals across

several life domains (e.g., physical, mental, academic, career, social); 2) develop several strategies to reach goals and overcome challenges (i.e., pathways thinking); and 3) maintain motivation (i.e., agency).^{14,15} Snyder's hope scale assesses individuals' self-reports of their pathways thinking (e.g., ability to strategize and navigate challenges) and agency (e.g., self-efficacy, motivation).^{14,15} Hope is associated with several positive outcomes (e.g., mental health, QOL, life meaning, coping with illness/pain) in the general population, cancer survivors, and other subpopulations,^{3,16-18} and hope-based interventions have shown effectiveness in improving these outcomes in general populations^{19,20} and YA cancer survivors.¹³ Acceptance and Commitment Therapy (ACT) aligns with hope, as ACT applies acceptance, mindfulness, commitment, and behavior change to hope-related constructs (e.g., goals, barriers, values)²¹ and can improve various outcomes (e.g., mental health, fear of recurrence) among cancer survivors.⁶⁻⁸

Also important, most survivorship interventions have been intensive^{22,23} and delivered in-person by licensed mental health specialists in healthcare settings.^{6,11,23} These rigorous approaches are commendable but limit scalability due to the intensive healthcare resources required and engagement barriers among YA survivors who are navigating several life demands.²⁻⁴ These limitations could be addressed by using health coaching and digital health. Health coaching incorporates evidence-based psychological interventions and has shown positive effects on various physiological, behavioral, psychological, and social outcomes,²⁴ as well as healthcare system outcomes (e.g., patient satisfaction).²⁵ Regarding digital approaches, a 2021 systematic review examining 29 systematic reviews of telemedicine interventions for cancer survivors (including 139 primary studies) indicated generally high feasibility, acceptability, adherence, and satisfaction,²⁶ however, of the 23 reviews including interventions with psychosocial outcomes, only one review included survivorship interventions for AYA survivors and only 4 studies in that review involved interventions addressing psychosocial outcomes (typically as secondary outcomes).²⁷

In summary, it is crucial to address YA survivors' psychosocial needs. Under-tapped opportunities to address these needs include focusing on positive outcomes, like hope, and leveraging scalable strategies like health coaching and digital approaches.

Objectives:

Primary Objectives: This 2-arm RCT addresses the primary objective of testing the feasibility and acceptability of AWARE (a digital intervention with health coaching that targets hope) compared to an AC among 155 YA cancer survivors.²⁸

Secondary Objectives: This 2-arm RCT addresses the secondary objective of testing the preliminary efficacy of AWARE (vs. an AC) in enhancing hope and QOL among 155 YA cancer survivors.²⁸

Study Design/Methodology:

Figure 1 provides an overview of this 2-arm RCT, involving a behavioral intervention (AWARE) and an AC. A total of 155 YA cancer survivors were enrolled in the study and randomized to AWARE (n=78) vs. AC (n=77). Participants were recruited, screened for eligibility, consented, and asked to complete the baseline survey. Both AWARE and the AC involved an 8-week intervention and control for non-specific intervention components. After the 8-week interventions, participants were immediately asked to complete the end-of-treatment (EOT; 8-week/2-month) follow-up assessment. At 16-weeks post-baseline, participants were asked to complete the final follow-up (FU; 16-week/4-month) assessment.

[figure not shown]

Figure 1. Study Overview

Study Population:

This study focuses on YA cancer survivors, targeting ~150 participants total randomized to AWARE vs. AC (1:1 randomization).

Inclusion Criteria: Inclusion criteria included: 18-39 years old, within 3 years of completing primary treatment or on maintenance chemotherapy, English-speaking, US resident, and smartphone access.

Exclusion Criteria: Exclusion criteria were: cancer recurrence since treatment completion, central nervous system cancer diagnosis (to ensure requisite cognitive functioning), in hospice, and prior diagnoses of alcohol/drug dependency, psychosis, bipolar disorder, or major depressive disorder.

Study Interventions:

Program Elements Consistent Across Conditions: AWARE was compared to an AC, designed to be parallel in terms of intervention platform (accessible on smart-device or computer), delivery (i.e., contact frequency), duration (i.e., number of weeks, session length), and certain components. Each involved 8 weekly sessions consisting of: 1) educational content via ~5-minute audio-recordings (and associated transcripts); 2) “reflections” (i.e., homework) to apply content to daily life; and 3) coaching sessions (which could be scheduled via the digital platform or during coaching calls) lasting ~15-30 minutes focused on the previous week’s content and reflections, education on new skills, and application to daily life. Coaches were trained and supervised by a licensed clinical psychologist, and recommended processes were used to ensure fidelity (i.e., tracking, audio-recorded session review, fidelity checklists, regular supervision).²⁹ Both programs also included a “resources” page with links to websites regarding various survivorship needs across life domains (e.g., financial, reproductive, mental health) and “wellness monitoring” (i.e., tracking happiness, motivation, sleep, physical activity, substance use). Additionally, the digital program sent email/text notifications for new sessions and coaching calls (up to 2 reminders/week).

Intervention (AWARE) Condition: AWARE aims to respond to cancer-related goal disruptions,³⁰ which particularly impact YA survivors,²⁻⁴ by enhancing goal-oriented thinking. Specifically, AWARE integrates elements from ACT²¹ and involves: 1) reassessing and reestablishing short- and long-term values-based, meaningful goals; 2) enhancing pathways thinking, including problem-solving skills, recognizing challenges, and reacting with flexibility; and 3) enhancing agency, for example, by promoting coping skills and effectively processing difficult thoughts and emotions in order to maintain motivation and self-efficacy. We hypothesized that AWARE will increase hope (i.e., goal-reorientation, pathways thinking, and agency), which may ultimately promote QOL.³¹ The first 4 AWARE sessions focused mainly on goals: (1) considering the cancer experience and its impact on identity and goals; (2) exploring values, self-identity, and goals; (3) reassessing and reestablishing short- and long-term values-based, meaningful goals across life domains; and (4) applying values and goals in relationships. The subsequent 3 sessions focus on pathways and agency: (5) experiencing and processing uncomfortable thoughts; (6) effectively navigating distressing thoughts and emotions; and (7) the utility of mindfulness and perspective when assessing goals and challenges. The final session (8) provided a program summary, opportunity for reflection, and strategies for ongoing application of program-related skills.

Attention Control (AC) Condition. The AC focused on nutrition and cancer,³² which is well-suited for an AC as it has participant relevance but is unrelated to efficacy outcome (hope). The AC involved an existing 6-session podcast with 3- to 5-minute audio-recordings addressing various nutrition-related topics for cancer survivors from reputable sources (e.g., cancer centers), supplemented with introduction and summary sessions to total 8 sessions.

Study Schedule and Timeline:

Participants were recruited in February–September 2024, with final data collection in February 2025. Participants are involved in an 8-week digital, coach-assisted intervention and asked to complete assessments at baseline and 2- and 4-month follow-up.

Survey data collection involved ~20-minute web-based assessments (via REDCap) at baseline, end-of-treatment (EOT; 8 weeks post-baseline), and follow-up (FU; 16 weeks post-baseline), with \$50 Amazon e-gift codes for completing each survey (up to \$150 total).

Feasibility and acceptability. Feasibility measures include: 1) accrual (recruitment of n=150); 2) retention at EOT and FU; and 3) program engagement, assessed via electronically captured program data regarding the number of weekly sessions viewed and reflections completed, and coach logs of coaching sessions completed.¹³

Acceptability measures include whether participants would recommend the program to friends who are cancer survivors (yes/no), as well as overall program satisfaction and helpfulness of each component (i.e., weekly educational recordings/transcripts, reflections, coaching, wellness monitoring, resources; 1=not at all to 5=very).¹³ We also asked about program frequency and length (about right, too frequent/long, not enough). We also assessed online program usability (i.e., program was easy to use, various functions were well integrated; 1=strongly disagree to 5=strongly agree; Cronbach's alpha=.90) and quality of coach interactions (i.e., my coach: was helpful, was friendly and warm towards me, showed genuine care about me and my experiences, listened to what I was saying, seemed to understand my thoughts/feelings, made me feel free to express myself, was not critical/judgmental; 1=strongly disagree to 5=strongly agree; Cronbach's alpha=.91). Additionally, we asked participants about alternative coaching channels (e.g., phone, text, email, opt-in for coaching only), barriers to coaching and overall program engagement (providing checklists of potential barriers and open-text fields for each), the program's most relevant or important aspects (open-ended), and potential

changes/additions (open-ended).³³

We pre-defined benchmarks for feasibility and acceptability: ≥75% completion/positive suggested no/minor revisions needed, 50-74% completion/positive required major revisions, and <50% suggested intervention failure.

Preliminary efficacy outcomes. Hope (primary efficacy outcome) was assessed using the Adult Hope Scale, which includes 4 agency items (e.g., "I energetically pursue my goals") and 4 pathways items (e.g., "I can think of many ways to get out of a jam") with responses (1=definitely false to 8=definitely true) yielding total scores of 8-64 and subscale scores of 4-32 (Cronbach's alpha=.90, .81, and .87).¹⁵

We used 2 measures of QOL (secondary efficacy outcome). To assess cancer-specific QOL, we administered the Functional Assessment of Cancer Therapy – General (FACT-G),³⁴ which includes subscales with 7 items each for physical, functional, and social well-being and 6-items for emotional well-being (Cronbach's alphas=.83, .83, .82, and .75). We also administered the 43-item Patient Reported Outcome Measurement Information System (PROMIS) Global Health Scale V2.0,³⁵ including subscales with 6 items each for physical functioning, fatigue, sleep disturbance, pain interference, ability to participate in social roles/activities, anxiety, and depression (Cronbach's alphas=.90, .94, .91, .96, .95, .93, and .93), and one item for pain intensity.

Covariates. Participants reported sociodemographic characteristics (e.g., age, sex, sexual orientation, ethnicity, race, education level, employment status, relationship status, parental status, health insurance) and cancer diagnosis/treatment factors (e.g., site and stage at diagnosis, treatments, date of diagnosis and treatment completion).

Statistical Analysis Plan:

Sample Size Determination: Assuming 80% power for sample size calculations, we targeted a sample size of n=150 to detect differences across conditions in key measures of feasibility and acceptability. Tests of efficacy in this pilot were secondary;³⁶ nonetheless, this sample size is sufficient to detect medium effects on hope (and secondary outcomes (based on the prior one-arm trial¹³), estimating ≥85% retention.

Data Analysis: Survey data were analyzed descriptively using SPSS V.27 with an alpha of .05. First, descriptive analyses characterized participants, and bivariate analyses (t-tests and ANOVAs for continuous variables, Chi-square tests for categorical) examined sociodemographics, health-related factors, and primary and secondary outcomes in relation to condition to determine any baseline differences.

Then, bivariate analyses assessed feasibility and acceptability outcomes. Next, responses to open-ended survey questions regarding acceptability were thematically analyzed using inductive analysis. Two coders reviewed responses and determined primary and secondary themes, which were then applied to an initial subset of surveys. The coders compared their codes to identify and resolve any discrepancies and clarify or revise themes and subthemes. After establishing high overall agreement (Kappa's>90%), the 2 coders independently coded the remainder of survey responses. Themes were organized into overarching domains alongside representative quotes.

We then assessed preliminary efficacy. Matched pairs t-tests assessed differences in hope and QOL measures from baseline to EOT and to FU among AWARE and AC participants, respectively. Preliminary bivariate analyses (Pearson correlations for continuous variables, t-tests and ANOVAs for categorical) explored factors associated with our outcome of interest (to identify potentially confounding variables to control for in multivariable analyses). Finally, we conducted multivariable

linear regression using block entry: 1) condition only; 2) condition and key sociodemographics (age, sex, education) and cancer-related factors (i.e., cancer stage, treatments, time since treatment completion); and 3) baseline outcome measures. There were minimal differences across the 3 models with regard to intervention effects; thus, we presented block 2, as baseline randomization yielded no differences by condition in hope or QOL outcomes, and hope and QOL scores over time were highly correlated with their respective baseline scores. We also explored program engagement levels in relation to changes in the primary hope outcome and interactions between baseline hope and condition on hope effects.

Informed Consent Process:

In February–September 2024, participants were recruited via BuildClinical, a third-party clinical trial recruiting system that helps investigators more efficiently recruit participants for clinical trials. BuildClinical uses machine learning and data mining procedures to recruit the target population from a variety of internet sources (e.g., Instagram, Facebook, Google). Ad content and placement targeted YA survivors, with specific considerations for men and diverse racial/ethnic minority groups. Individuals who clicked on ads were sent to a webpage describing the study. Interested and potentially eligible participants authorized BuildClinical to provide their contact information to the study team, who then contacted them via email, text, and/or phone to obtain consent, confirm eligibility, and administer the web-based baseline survey. After completing the baseline survey, participants were randomized to AWARE or AC (using a pre-determined blocked random number sequence). Participant randomization was stratified by sex (due to different cancer types by sex) and age (18-29, 30-39, given potential developmental differences).

Privacy and Confidentiality:

To minimize risks to confidentiality, study data are protected with all appropriate physical and operational security protections. All data files use encryption and strong password protection. Access to data is on a role-based standard; only those study staff who require access to identifying data to complete their study-related roles are allowed access. REDCap, the electronic platform for self-interview, is HIPPA compliant. We also remind participants before each survey begins to only take the survey in a private area, where he/she will not be observed.

We also developed procedures to minimize indirect disclosure of participation in this study. For each mode of contact information, we asked specifically whether anyone else potentially has access to that mode of communication, and if it was acceptable to leave a non-specific message about participation in a health study. No study-related messages were ever mention the nature of the research study. Additionally, all scripts for email, text message, and telephone contact with participants were reviewed and approved by the GW IRB before being used for contact with participants. All study staff were trained in security and confidentiality procedures.

All researchers involved were required to be trained in the importance of patient confidentiality and de-identification of data as well as HIPAA and Good Clinical Practice requirements. Staff were trained through GW HIPAA training protocol offered via www.CITIprogram.org. Study staff were trained upon confidentiality standards and proper interviewing/coaching techniques. Staff training is comprehensive and will surround not only confidentiality but respect for persons, safety, the intervention, testing, and all related components of the study. The MPIs oversaw and ensured ongoing respect for participants and their data throughout the study.

Risk/Benefit:

Risk to Participants: The potential risks to participants are minimal. Some participants may be uncomfortable answering personal questions. Participants will be told that they have the right to refuse to answer sensitive questions. It is also possible for someone participating in online data collection could be identified as a research participant, but this is uncommon.³⁷ There is some risk that those completing surveys via smartphones could be observed if they complete the surveys in public or that data could be at risk during transmission.

Benefits to Participants: The potential benefits from participation in this intervention include improvement in hope, psychosocial distress, and QOL. For control participants, benefits relate to the contributed knowledge from the study results, as well as increased knowledge of financial management.

Furthermore, knowledge gained from this project will be used to design a more detailed phone-based hope intervention for YA cancer survivors completing treatment and undergoing major life transitions. In view of the potential information to be gained, and how it will ultimately be able to contribute to new approaches to providing care to this survivor population, the minimal risks do not outweigh the potential for benefit.

Data Safety Monitoring & Adverse Event Reporting:

The safety of our study participants is paramount. The following mechanisms were put in place throughout the study.

Potential Adverse Events Resulting from Participation: Adverse events include potential violation of confidentiality; possible discomfort or embarrassment in disclosing sensitive information; possible dissatisfaction with the intervention programs or study activities; possible embarrassment or fear in discussing experiences with cancer.

Procedures to Safeguard Against Adverse Events: The Institutional Review Board (IRB) at GW reviewed the protocol and all study materials, including consent documents and recruitment materials before the study begins. Quality control procedures include creation of a manual of operations and tracking procedures, and maintenance of personal identifiers in locked files and in keyword-protected computer files. Data is shared only among the research team and contains only study identification numbers, without identifying information.

Informed consent: All participants will be required to complete informed consent prior to participation. The potential participants are informed about the voluntary nature of the study and their rights to refuse or withdraw without consequence. [name] and the study coordinator trained in human subjects protection are available throughout the study to address participant concerns about study procedures. If either PI determines that potential participants exhibit comprehension difficulties, extra guidance will be provided to make sure they feel fully informed about the study. Participants will be encouraged to call the PI and/or the GW IRB for questions or clarification.

Confidentiality safeguards. All participants were assigned a study ID used on any communication. Codes linking the study ID to participant identities remain in a secured server; no identifying information are maintained in the participant file. Individual data and names are never attached in any way. Data were collected by trained, NIH/HIPAA certified project personnel. Data were entered into a computerized data base (REDCap) with assigned codes/id numbers only. Computers are maintained in a locked area. Only research team members have access to the computerized or stored data.

Dissatisfaction safeguards. Participants were encouraged to discuss with the PI any possible dissatisfaction with the intervention or assessment activities.

Data and Safety Monitoring Plan. The monitoring plan addresses: safety of participants, reporting of adverse events, validity and integrity of the data, enrollment rate relative to expectation, retention of participants and adherence to protocol, and data completeness.

Data. All quantitative data were entered into REDCap (research electronic data capture). The monitoring of the progress of the clinical trial and the safety of participants were performed by the study team and Data and Safety Monitoring Board. A four-person board of individuals not involved in the study (including those with expertise in adolescent or young adult oncology, qualitative data collection, epidemiology, and biostatistics) was created to monitor for data integrity and safety, and met quarterly.

Safety. The PIs are responsible for following adverse event reporting requirements as outlined below. These responsibilities include: a) reviewing the accuracy and completeness of all adverse events reported; b) compliance with IRB policies for reporting adverse events and/or serious adverse events; and c) closely monitoring research participants at each point of contact for any new adverse events or serious adverse events. A serious adverse event is any untoward medical occurrence that: results in death; is life-threatening; requires in-patient hospitalization or prolongation of existing hospitalization; results in persistent or significant disability or incapacity; is a congenital anomaly/birth defect; an event that requires intervention to prevent permanent impairment or damage; or important medical events that do not result in death, are not life-threatening, or do not require hospitalization may be considered serious adverse events when, based upon appropriate medical judgment, they might jeopardize the subject and might require medical or surgical intervention to prevent one of the outcomes listed above.

The grading of adverse events used the scale below: 0=no adverse event or within normal limits; 1=mild adverse event; 2=moderate adverse event; 3=severe adverse event resulting in hospitalization or prolongation of existing hospitalization, a persistent or significant disability/incapacity, or a congenital anomaly/birth defect; 4=life-threatening or disabling adverse event; and 5=fatal adverse event.

Although this study is of low to moderate risk and no serious adverse events were expected, we ensured that all adverse events are reported and properly addressed. 1) Serious unanticipated events were to be reported within 24 hours to the GW IRB. 2) An adverse event report including a description of the event, when the event occurred, and when and how the event was reported, was to be generated for each event. 3) The study PIs were to conduct a review of all adverse events upon completion of every study subject. They were to evaluate the frequency and severity of the adverse event(s) and, in conjunction with the DSMB and the IRB at GWU, were to determine if modifications to the protocol or consent forms are required. 4) A report to the IRB was to be made at a minimum of once every 6 months, including when re-approval for the protocol is sought. The IRB was to evaluate whether the study should continue unchanged, require modification, continue, or close to enrollment. If increased frequency of serious adverse events were detected and reported, an ad hoc safety review was to be convened to determine whether and how to modify, continue, or terminate enrollment.

In this study, no adverse events were reported.

Conflict of Interest:

The investigators declare no conflicts of interest.

Publication and Presentation Plans:

Study findings have been disseminated via peer-reviewed journal articles and scientific conferences.

Peer-reviewed Journal Articles (published, in press, under review):

1. [name], [name], [name], [name], [name], [name], [name], [name], & [name] (2024). A digital, coach-assisted intervention to address the psychosocial needs of young adult cancer survivors: randomized controlled trial protocol and intervention adaptation process. *Contemporary Clinical Trials*, 141, 107545.
2. [name], [name], [name], [name], [name], [name], [name], [name], [name], & [name] (2024). Young adult cancer survivors' perspectives on cancer's impact on different life areas post-treatment: A qualitative study. *Journal of Adolescent and Young Adult Oncology*, 13(5), 748-759.
3. [name], [name], [name], [name], & [name] (2025). Cannabis use among adolescents and young adults with cancer: A scoping review. *Journal of Cancer Education*, doi: 10.1007/s13187-025-02693-0. Online ahead of print.

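### The presented between-arm model (block 2) leaves out the baseline outcome, and the high correlation given as a reason is a reason to include it; block 3, already fitted, is the more precise model.

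*Combined protocol and SAP*

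**What the plan says.** The efficacy objective (Objectives, Secondary Objectives) is comparative: "testing the preliminary efficacy of AWARE (vs. an AC) in enhancing hope and QOL". Under Sample Size Determination, "Tests of efficacy in this pilot were secondary", yet "this sample size is sufficient to detect medium effects on hope", with 80% power, a target of 150 and at least 85% retention.

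Under Data Analysis, the efficacy work has three steps.

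- Within-arm comparisons: "Matched pairs t-tests assessed differences in hope and QOL measures from baseline to EOT and to FU among AWARE and AC participants, respectively".
- Bivariate screening for factors associated with the outcome, to find variables to control for.
- A linear regression by block entry. Block 1 has condition only. Block 2 adds age, sex, education, cancer stage, treatments and time since treatment completion. Block 3 adds the baseline outcome.

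All three models were fitted: "There were minimal differences across the 3 models with regard to intervention effects; thus, we presented block 2". The further reasons given are that the arms did not differ at baseline in hope or QOL, and that "hope and QOL scores over time were highly correlated with their respective baseline scores". The section does not say whether the dependent variable is the follow-up score or the change from baseline. The survey analyses as a whole are introduced with "Survey data were analyzed descriptively using SPSS V.27 with an alpha of .05".

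**The concern.** Two of the stated reasons for presenting block 2 do not support it.

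First, a high correlation between baseline and later scores means that baseline explains much of the outcome variance. Including it removes that variance from the error term of the condition effect. The plan's own screening step looks for factors associated with the outcome in order to control for them, and by its own account the baseline score is such a factor.

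Second, finding no significant baseline difference does not show that the arms were balanced. It shows only that any imbalance was too small to reach .05 in that sample.

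The remaining reason, minimal differences in intervention effects across models, concerns the effects. The text does not say that standard errors or confidence intervals agreed as well.

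At stake is the precision of the randomised comparison that readers will use to judge preliminary efficacy. The unnamed dependent variable adds to this, because without baseline in the model the follow-up-score and change versions of block 2 are different estimates with different precision.

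**Working it through.** **Inputs from the documents.** Target 150; retention at least 85%; power 80%; alpha .05; 1:1 allocation; 78 and 77 randomised.

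**Assumptions.** Two-sided testing; a medium effect is 0.5 SD; equal variances at baseline and follow-up; correlation r between baseline and follow-up score, given the block 2 covariates, of .5 to .8. If r is read as a raw correlation, the gains below are upper guides, because the covariates may already explain part of the same variance.

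**Step 1. Reproduce the planned size.** n per arm = 2(1.960 + 0.842)² / 0.5² = 62.8, so 63, giving 126 in total; 126 / 0.85 = 148.2, so 149. The t-based version gives 64 per arm, 128 in total; 128 / 0.85 = 150.6, so 151. Both agree with 150. The plan's figure is therefore consistent with a between-arm comparison that is not adjusted for baseline.

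**Step 2. Completers.** 150 × 0.85 / 2 = 63.75, taken as 64 per arm. For a two-sample t-test at 80% power, the detectable difference without baseline is 0.499 SD.

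**Step 3. Block 3 against block 2.** Write SD for the standard deviation of the follow-up score given the covariates.

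- Residual SD with baseline in the model: SD × √(1 − r²), for either outcome.
- Without baseline, follow-up score: SD. The ratio of standard errors is √(1 − r²).
- Without baseline, change: SD × √(2(1 − r)). The ratio is √(1 − r²) / √(2(1 − r)) = √((1 + r)/2).
- Detectable difference: 0.499 times the relevant factor.

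| r | SE ratio, follow-up score | SE ratio, change | Block 2 detectable, follow-up score | Block 2 detectable, change | Block 3 detectable, either |
|---|---|---|---|---|---|
| .5 | 0.87 | 0.87 | 0.50 | 0.50 | 0.43 |
| .6 | 0.80 | 0.89 | 0.50 | 0.45 | 0.40 |
| .7 | 0.71 | 0.92 | 0.50 | 0.39 | 0.36 |
| .8 | 0.60 | 0.95 | 0.50 | 0.32 | 0.30 |

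A simulation with ordinary least squares agreed: at r = .5 the ratios were 0.869 and 0.869, and at r = .8 they were 0.603 and 0.953.

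**Step 4. What a non-significant baseline test leaves open.** With 78 and 77 randomised, the standard error of a baseline difference in SD units is √(1/78 + 1/77) = 0.161. Differences up to about 1.96 × 0.161 = 0.31 SD are not significant. A difference of that size would move an unadjusted follow-up-score comparison by r × 0.31, which is 0.16 SD at r = .5 and 0.25 SD at r = .8. This is a limit, not an estimate for this trial; the reported closeness of the three models suggests that the actual shift was small.

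**Step 5. The outcome definition.** If follow-up = a + b × condition + c × baseline, then follow-up − baseline = a + b × condition + (c − 1) × baseline. The condition coefficient b is the same, so block 3 gives one answer whichever outcome was used.

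**The case against.** The strongest reply is that nothing is biased. Under randomisation, leaving out baseline does not shift the effect on average, and the plan reports that the effects hardly differed across models. The loss of precision widens intervals; it does not manufacture a benefit. Block 2 also delivers about the power that the sample size implies, as Step 1 shows. If the outcome is change, the gain from block 3 is modest: the detectable difference improves by 0.07 SD at r = .5 and by 0.02 SD at r = .8. Efficacy is secondary in this pilot, and no decision rule depends on an efficacy p-value. Moving to block 3 now would also be a model choice made after the results.

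All of this stands and limits the size of the point. It does not rescue the stated rationale, and it does not show that block 2 is as informative as block 3. The post hoc objection is met by disclosure and by showing all three blocks.

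A reader might infer something stronger from the paired t-tests, which come first under preliminary efficacy: that a significant change in AWARE with none in AC was taken as efficacy. That inference would be unsound. With equal true change in both arms and 64 completers each, the pattern arises in up to about 25% of trials per outcome and time point (at a standardised change of 0.25), but in only 2.4% when neither arm changes. The documents state no such rule, however. They contain and present a between-arm model and speak of intervention effects only in connection with it. Order of description is not rank, so these rates do not measure a defect of this plan.

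**Conclusion.** The point holds as one of precision and rationale. The presented model omits a covariate that the plan itself describes as highly correlated with the outcome, and gives that correlation as a ground for the omission. The cost is a standard error that block 3 would multiply by 0.87 to 0.60 (follow-up score) or 0.87 to 0.95 (change), plus chance imbalance left uncorrected. These sizes rest on assumed correlations of .5 to .8, equal variances, two-sided testing and 64 completers per arm; the direction holds under either outcome at every r considered.

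The documents do not support a claim that the effect estimate is biased on average, that block 2 was chosen because it favoured AWARE, or that efficacy was concluded from within-arm tests. The change should be made, but it concerns how a secondary objective is reported, not the validity of the trial.

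**What to change.** For hope and QOL at EOT and FU, present the AWARE-versus-AC condition coefficient with its 95% CI from block 3, and show blocks 1 and 2 beside it so that readers can compare estimates and intervals. Name the regression outcome. Replace the present rationale with a statement that baseline is included because it is strongly related to the outcome, and that block 3 was chosen for presentation after the results had been seen. As a minor addition, label the within-arm paired comparisons as descriptive.

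The cost is wording and tables only: baseline scores are collected and block 3 is fitted. The schedule puts the trial past collection ("with final data collection in February 2025"), and the publication list shows an outcomes paper under review and a November 2025 conference presentation. The change therefore falls on reporting. The downside is that a different fitted model is presented, and it must carry a post hoc label.
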